6.14.2 Optical Coherence Tomography

The mean change from baseline to month 12 in Central Retinal Thickness determined with Optical Coherence Tomography for both eyes will be calculated for both groups and will be compared using the Mann Whitney u test.

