2.2 Secondary objectives

- to compare mean change in CRT at 12th month from baseline between two groups with OCT
- to assess the number of injections needed over a 12-month treatment period with a “wait and extend” dosing regimen
- to assess the number of visits needed over a 12-month treatment period with a “wait and extend” dosing regimen
- to evaluate the number of patients with improvement in BCVA from baseline
- to evaluate the number of patients with improvement of 5 or more letters from baseline
- to evaluate the number of patients with improvement of 10 or more letters from baseline
- to evaluate the number of patients with improvement of 15 or more letters from baseline
- to evaluate the safety of intravitreal injections of Lucentis (ranibizumab) in patients with DME
- to describe the change in Patient reported functional ability of Lucentis-treated patients.

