3.1 Study design

This is a randomized controlled, multicenter, 12 month study of Lucentis (ranibizumab) that the consenting patients will participate in a screening period and will be evaluated for their eligibility to enroll the study. After the screening period and the eligibility assessment of the patient, only one eye will be selected / treated as the study eye. After eligibility confirmation at baseline, patients will be randomized into one of the treatment arms as below:

- Arm 1 - Labeled regime arm: Treatment will be given monthly and will be continued until maximum visual acuity is achieved (the patient's visual acuity is stable for three consecutive monthly assessments performed while on ranibizumab treatment). Thereafter patients should be monitored monthly for visual acuity.
- Retreatment criteria:
 - According to this protocol VA stability means BCVA \geq 84 letters (approximate Snellen equivalent of 20/20) or OCT <300 microns in the last 2 consecutive visits or no improvement can be achieved according to the investigators evaluation regarding VA and OCT measures in the last 2 visits . Stable patients do not require reinjection and should be evaluated in the next visit for reinjection.
 - If VA decreases \geq 5 letters compared to previous visit and OCT is >300 microns, patients will be retreated.
 - If VA decreases \geq 5 letters compared to the previous visit or CRT increases >50 microns compared to the previous visit, patients will be retreated.
 - After 3 monthly injections of the investigational drug laser photocoagulation can be administered if VA worsens \geq 10 letters and/or CRT increases >100 microns.
- The interval between two doses should not be shorter than 1 month.
- Arm 2 - Wait and Extend regime arm: Lucentis (ranibizumab) 0.5 mg will be injected subsequently at baseline, month 1 and 2. After the three initial loading doses, patients will be called for the control visits 1 month later. If the visual acuity has reached a stable level and there is no sign of edema on OCT, patients will not receive intravitreal injection and will be called to come back 6 weeks later. The interval is increased by 2 weeks until a maximum of 8 weeks as long as the patient presents as stable regarding visual acuity, central retinal thickness and clinical findings. If there is a negative change, the interval is shortened back to 4 weeks.

Retreatment criteria:

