4.1 Inclusion criteria

Patients eligible for inclusion in this study have to fulfill **all** of the following criteria:

1. Written informed consent must be obtained before any assessment is performed.
2. Male or female patients >18 years of age who have signed an informed consent
3. Patients with Type 1 or Type 2 diabetes mellitus (according to ADA or WHO guidelines) with HbA1c not more than 12.0% at screening (Visit 1). Patients should be on diet, exercise, and/or pharmacological treatment for diabetes.
4. Patients with visual impairment due to focal or diffuse macular edema with center involvement in at least one eye, as demonstrated with color fundus photography, fluorescein angiography and OCT within 28 days of the baseline treatment. If both eyes are eligible, the one with the worse visual acuity, as assessed at Visit 1, will be selected for study treatment unless, based on medical reasons, the investigator deems the other eye the more appropriate candidate for study treatment. The study eye must fulfill the following criteria at Visit 1:
 - BCVA score between 78 and 39 letters, inclusively, using ETDRS-like visual acuity testing charts at a testing distance of 4 meters (approximate Snellen equivalent of 20/32 to 20/160)
 - Decrease in vision is due to DME and not due to other causes, in the opinion of the investigator

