5.4 Treatment blinding

The study is an open label study so there are no blinding procedures applicable.

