5.5.8 Prohibited Treatment

Any concomitant medications including prescription drugs or over-the-counter preparations used by a patient during the study and until the conclusion of the study participation (except for routine medications given for ocular procedures required by the protocol, i.e. fluorescein, dilating drops, topical antibiotic, topical anesthetic) must be recorded on the Concomitant medications/Significant non-drug therapies CRF including start and stop dates and reason for use.

Laser photocoagulation for DME is permitted only as rescue treatment according to predefined criteria and needs to be

recorded on the Concomitant medications/Significant non-drug therapies CRF

Use of the following treatments is NOT allowed after the start of the study:

- Chronic concomitant therapy with topical ocular corticosteroids
- Other intravitreal medication in the study eye
- Systemic medications known to be toxic to the lens, retina or optic nerve, including Deferoxamine, Chloroquine/ hydroxychloroquine (Plaquenil), Tamoxifen, Phenothiazines and Ethambutol
- Treatment with glitazones during the study.
- Any other investigational drug

The below treatments will be prohibited 30 days before randomisation: verteporfin (Visudyne®), external beam radiation treatment, , submacular surgery or other surgical interventions for DME.

The below treatments will be prohibited 90 days before randomisation: focal laser photocoagulation treatment.

The below treatments will be prohibited 120 days before randomisation: macular laser photocoagulation treatment.

During the study, below treatment will be permitted: Retrobulber anesthesia to prevent eye movements, metochloropamide or other treatments for preventing the nausea due to fluorescein injection and other routine treatments for glaucoma. The patient will also be provided an additional topical antimicrobial medication to use 3 days after the injection which will be used 4 times a day.

If the investigator decided that the other eye (other than the study eye) has a DME lesion or has a new DME lesion occurred during the study which needs treatment, appropriate routine ranibizumab treatment will be applied by the investigator; however any data will not be collected for the other eye. The ranibizumab treatment applied to the other eye will be given by NOVARTIS.

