9.5 Analysis of secondary variables

9.5.1 Efficacy variables

- Mean change in CRT (μm) by Optical coherence tomography at 12th month from baseline
- Mean no. of injections over a 12-month treatment period
- Mean no. of visits over a 12-month treatment period
- Proportion of patients who gained ≥ 0 , ≥ 5 , ≥ 10 and ≥ 15 letters in BCVA at 12th month
- Incidence of adverse events (AEs) and serious AEs (SAEs), by ophthalmic examinations and IOP measurements, and by changes in vital signs and laboratory parameters over the 12-month assessment period.
- Mean change in VFQ25 scores at 12th month from baseline

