3.2. SECONDARY OBJECTIVES

- To compare the mean change in CRT from baseline at month 12 between the two groups using OCT
- To evaluate the number of injections required for a treatment period of 12 months with a “wait and extend” dosing regimen
- To evaluate the number of visits required for a treatment period of 12 months with a “wait and extend” dosing regimen
- To evaluate the number of patients with improvement in BCVA from baseline
- To evaluate the number of patients with improvement of 5 or more letters from baseline
- To evaluate the number of patients with improvement of 10 or more letters from baseline
- To evaluate the number of patients with improvement of 15 or more letters from baseline
- To evaluate the safety of intravitreal Lucentis (ranibizumab) injections in patients with DME
- To describe patient-reported change in functional ability in patients treated with Lucentis

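### The only between-arm test of month-12 central retinal thickness (SAP 6.14.2) is written for both eyes and does not say how the eyes are handled, although only the study eye is on the randomised regimen

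*SAP*

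**What the plan says.** **The test.** Under SAP 6.14.2, the month-12 CRT change "determined with Optical Coherence Tomography for both eyes will be calculated for both groups and will be compared using the Mann Whitney u test". No other section of the SAP tests CRT between arms. SAP 6.11 only tabulates central thickness by arm, again for both eyes.

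**The objective and variable.** Protocol 2.2 lists first among the secondary objectives "to compare mean change in CRT at 12th month from baseline between two groups with OCT". SAP 3.2 repeats it: "To compare the mean change in CRT from baseline at month 12 between the two groups using OCT". Protocol 9.5.1 defines the variable as mean change in CRT "by Optical coherence tomography at 12th month from baseline". None of the three names an eye.

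**Which eye is randomised.** Protocol 3.1 says that "only one eye will be selected / treated as the study eye", and SAP 4 says the same. SAP 6.2 counts study eyes as right or left, so the study eye is known for each patient.

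**The fellow eye.** Protocol 4.1 requires "macular edema with center involvement in at least one eye", so the other eye may be unaffected. If the other eye has or develops edema that needs treatment, Protocol 5.5.8 says that "appropriate routine ranibizumab treatment will be applied by the investigator; however any data will not be collected for the other eye". Protocol 6.4 has OCT done on both eyes. On masking, Protocol 5.4 says: "The study is an open label study so there are no blinding procedures applicable".

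**Layout elsewhere.** SAP 6.8.1 (biomicroscopy) and 6.12 (angiography) report right and left eyes, not study and fellow eyes.

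**The concern.** The objective is a comparison of two regimens, and only the study eye receives one of them. A fellow eye either has no disease to respond or is treated outside both regimens. Its CRT change is therefore not an outcome of the randomised contrast, yet the test as written includes it.

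The analyst has to choose how to handle the eyes, and in an open-label trial that choice could be made with knowledge of the data. Several available choices do not estimate the study-eye effect. A diluted CRT difference could also be read as anatomical similarity, in a trial whose aim is to show that the regimens are comparable.

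**Working it through.** **The plan's own figure.** The documents give no effect, SD, alpha or power for CRT. Their only power statement is for visual acuity (Protocol 9.7, SAP 5.1): margin 5 letters, SD 7, alpha 0.025, 90% power, 43 per arm. The normal formula gives 2 × 7² × (1.96 + 1.28)² / 5² ≈ 41.2, so 42 per arm. With the t distribution, 42 per arm gives 89.9% and 43 gives 90.6%. The stated 43 reproduces and is not in question here. It says nothing about CRT power.

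**Possible readings of 6.14.2**

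| Reading | Estimates the study-eye effect? | Support in the SAP |
|---|---|---|
| Study eye and fellow eye tested separately | Yes, in the study-eye test | Not stated |
| Right eye and left eye tested separately | No; each side mixes study and fellow eyes | Layout of 6.8.1 and 6.12 |
| Two eyes averaged per patient | No, unless the fellow eye happens to show the same difference | Not stated |
| Two eyes stacked as separate observations | No; also ignores inter-eye correlation | Not stated |
| Both-eyes phrase describes imaging only | Undetermined; the test then names no eye | Protocol 6.4 images both eyes |

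**Assumed inputs, for illustration only**
- ds and df: between-arm difference in the study eye and in the fellow eye. The figures below take df = 0.
- k: fellow-eye SD divided by study-eye SD, taken as 1/3 or 1.
- ρ: inter-eye correlation of CRT change, taken as 0 to 0.5.
- Two-sided alpha 0.05, and an effect that gives a study-eye test 80% power. The power formula is a normal approximation.

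**Averaged eyes.** The contrast is (ds + df)/2, which is ds/2 when df = 0. In units of study-eye variance, the average has variance (1 + k² + 2ρk)/4. To keep the same power, the number of patients must be multiplied by

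R = [(1 + k² + 2ρk)/4] / (1/2)² = 1 + k² + 2ρk.

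Power at the unchanged sample size is Φ((1.96 + 0.84)/√R − 1.96).

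| k | ρ | R | Power (from 80%) |
|---|---|---|---|
| 1/3 | 0 | 1.11 | 76% |
| 1/3 | 0.3 | 1.31 | 69% |
| 1/3 | 0.5 | 1.44 | 65% |
| 1 | 0 | 2.00 | 51% |
| 1 | 0.3 | 2.60 | 41% |
| 1 | 0.5 | 3.00 | 37% |

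**Right/left tests.** Suppose half the eyes on each side are study eyes. The contrast per side is ds/2. The variance is at least (1 + k²)/2, because any difference in mean change between study and fellow eyes adds to it. So R ≥ [(1 + k²)/2] / (1/2)² = 2(1 + k²):
- k = 1/3: R ≥ 2.22, per-side power at most 47%.
- k = 1: R ≥ 4.00, per-side power at most 29%.

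**Stacked eyes.** The test treats two correlated values from one patient as independent. The effect on type I error depends on the assumed correlation and on how far study and fellow eyes differ in mean change, so no figure or direction is given.

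**Separate study-eye and fellow-eye tests.** The study-eye test has one value per patient and loses nothing.

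**The case against.** The best defence is that the text is ambiguous, not wrong. Calculating the change for both eyes most naturally means eye by eye. No passage mentions averaging or stacking, the study eye is recorded, and a sensible analyst would report it. CRT is a secondary endpoint with no sample-size basis, and every power figure above rests on assumed values.

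Much of this stands. The harm is conditional on how the eyes are handled, and its size cannot be fixed from the documents. But the eye-by-eye layout that the SAP itself uses is right and left, which is not a study-eye test. Taking the study eye alone departs from the written words. If the phrase only describes imaging, the test names no eye, and the gap remains.

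A reader might infer more, in three ways that the documents do not support:

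- **That the primary visual acuity test has the same fault.** SAP 6.14.1 does not say both eyes, and its responder comparisons count patients. SAP 6.9 mentions both eyes when describing the tabulation, and the paired test there is within arm.
- **That the result is biased in a known direction.** Halving holds only for averaging or an even right/left mix with no fellow-eye difference. Fellow-eye treatment is decided by an unmasked investigator and could differ by arm in either direction.
- **That Protocol 5.5.8 rules out fellow-eye OCT data, against Protocol 6.4.** The sentence in 5.5.8 may refer only to treatment data. It could be clarified, but this point does not rest on it.

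**Conclusion.** The point holds for the secondary CRT comparison. SAP 6.14.2 brings both eyes into the only between-arm CRT test, without a study-eye restriction or a rule for handling the eyes, and nothing elsewhere in the protocol or SAP supplies one. That finding rests on the text alone and is firm.

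The size of the harm is less certain. With averaged eyes and no fellow-eye difference, 80% power falls to about 65–76% at an SD ratio of 1/3, or 37–51% at a ratio of 1. With right/left tests, the per-side ceiling is about 47% or 29%. These are illustrations under assumed SD ratios and correlations, and there is no loss if the study eye is tested on its own.

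Neither the primary visual acuity conclusion nor the sample size is shown to be affected. The wording should be corrected before analysis.

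**What to change.** In SAP 6.14.2, replace *for both eyes* with *for the study eye, one value per patient*. Keep fellow-eye OCT descriptive, as SAP 6.11 already plans, and label eyes as study eye and fellow eye there.

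Optionally, for consistency, name the study eye in SAP 6.14.1 and in the within-arm paired test in 6.9. That is a clarification, not the correction of an error.

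The cost is one phrase in 6.14.2 and, if wanted, matching phrases in the other sections. No new data are needed, because the study eye is already recorded for each patient (SAP 6.2).

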6.14.3 Injection and Visits

The number of injections and visits required for a treatment period of 12 months with a “wait and extend” dosing regimen will be evaluated.

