Ranibizumab (Lucentis) is a recombinant humanized IgG1 κ isotype monoclonal antibody fragment (Fab) that selectively binds VEGF. Ranibizumab (intravitreal injections of 0.5 mg) is approved for the treatment of neovascular age-related macular degeneration (AMD), the treatment of visual impairment due to diabetic macular edema (DME) and the treatment of

visual impairment due to macular edema secondary to retinal vein occlusion (branch RVO or central RVO) in a number of countries worldwide [Product information].

Five trials, ie, two DRCR.net trials, RESTORE, RISE, and RIDE, have provided level I evidence supporting use of ranibizumab for the treatment of DME, and two additional trials have provided level II evidence. These trials demonstrate that ranibizumab therapy for DME is safe and effective for two years [Stewart, 2013] The approval of ranibizumab for patients with visual impairment due to DME with center involvement has improved the visual prognosis and offers therapy for an up to now unmet medical need [Lang, 2012].

The recommended dose for Lucentis is 0.5 mg given monthly as a single intravitreal injection.

Treatment is continued until maximum visual acuity is achieved i.e the patient's visual acuity is stable for three consecutive monthly assessments performed while on ranibizumab treatment. Thereafter patients should be monitored monthly for visual acuity. Treatment is resumed when monitoring indicates loss of visual acuity due to DME. Monthly injections should then be administered until stable visual acuity is reached again for three consecutive monthly assessments. The interval between two doses should not be shorter than 1 month. However, there is a need to explore a more clinical feasible treatment regime to provide satisfactory treatment effect with a lower number of visits and injections [Product information]

A "wait and extend" regimen has been demonstrated efficient for treatment of wAMD in SALUTE study as mentioned above and found to be safe and tolerable [ASRS 2013]. The rationale of this pilot study is to show that similar approach is applicable in treatment of DME.

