9.3 Treatments

Descriptive statistics will be given for application of the study medication. To evaluate the dosage compliance, the percent range of the patient that accepted fully complied will be given. Concomitant medication/significant non-drug treatments will be summarized as numbers and per cents.

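### Injections and visits are to be evaluated only for wait and extend; no between-arm difference or confidence interval is planned, which matters most for injections

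*SAP*

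**What the plan says.** **Rationale.** Protocol 1.1 says a more feasible regimen is needed "to provide satisfactory treatment effect with a lower number of visits and injections". The synopsis gives the same reason.

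**Objectives.** Protocol 2.2 sets out "to assess the number of injections needed over a 12-month treatment period with a" wait-and-extend schedule and, in parallel, "to assess the number of visits needed over a 12-month treatment period with a" wait-and-extend schedule. SAP 3.2 repeats both. Neither objective mentions the labelled arm.

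**Variables.** Protocol 9.5.1 lists "Mean no. of injections over a 12-month treatment period" and "Mean no. of visits over a 12-month treatment period". There is no arm restriction and no method of comparison.

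**Analysis.** The whole of SAP 6.14.3 is one sentence. It begins "The number of injections and visits required for a treatment period of 12 months" and ends "with a “wait and extend” dosing regimen will be evaluated". It names no statistic, comparator, difference or interval. The two sections before it, SAP 6.14.1 and 6.14.2, do compare the groups, on BCVA and on central retinal thickness.

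**Related text.** Protocol 9.3 states "Descriptive statistics will be given for application of the study medication", again without an arm restriction. The opening of SAP section 6 plans a table of visit attendance by treatment group, as n and %.

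**The concern.** If the trial shows non-inferior vision, the argument for the new regimen then rests on its costing the patient less. That is a comparative statement and needs the labelled arm's figures beside the wait-and-extend figures. Protocol 1.1 cites the earlier AMD study for exactly such a comparison: fewer visits in the wait-and-extend group than in its comparator.

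Followed as written, the SAP gives a wait-and-extend injection count and no labelled-arm count to set against it. The labelled regimen is not a fixed monthly course either. Injections stop when the patient is stable and resume on deterioration, and protocol 3.1 lists the same retreatment criteria under both arms. The size of any injection difference, and even its direction, therefore cannot be read from one arm. A comparison added after the data are seen, in an open-label trial, would carry less weight than one specified now.

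**Working it through.** **1. What the documents plan for each count**

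| Source | Injections | Visits | Between-arm estimate |
|---|---|---|---|
| Protocol 2.2, SAP 3.2 (objectives) | wait and extend only | wait and extend only | none |
| Protocol 9.5.1 (variables) | mean, no arm limit | mean, no arm limit | none |
| Protocol 9.3 | descriptive, no arm limit | not covered | none |
| SAP section 6, opening | not covered | attendance by group, n and % | none |
| SAP 6.14.3 | wait and extend only | wait and extend only | none |

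SAP 6.1 to 6.13 contain no exposure or injection table, so nothing in the SAP carries out protocol 9.3.

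**2. Visits: what can be inferred from the schedule**

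- Labelled arm: visits 1 to 14, with visit 14 at month 12 (protocol 3.1, 5.5.10 and the section 6 table). Planned count: 14.
- Wait and extend, patient stable throughout: screening, then days 0, 30, 60 and 90. The next visit is 6 weeks later (90 + 42 = 132), then every 8 weeks: 132 + 56 = 188, then 244, 300 and 356. Day 356 lies within the 7-day window around day 360. Planned count: 10.
- Largest planned saving: 14 − 10 = 4 visits, or 4/14 = 29%. Any return to 4-week intervals reduces it.

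Actual counts can differ from planned ones through missed visits, early exit (20% drop-out is assumed in protocol 9.7) and unscheduled visits (note c to the schedule).

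**3. Injections: no equivalent inference**

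The schedule fixes only the first three wait-and-extend injections (baseline, months 1 and 2). Later injections in that arm, and labelled-arm injections beyond the initial monthly course, depend on response. No document gives an expected count for either arm.

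**4. Precision of a between-arm difference in mean injections**

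The documents state no figure for injections or visits, so there is none to reproduce. The sample size used here does reproduce: with margin 5, SD 7, one-sided 0.025 and 43 per arm, the noncentral t calculation gives power 0.906 against the stated 90% (protocol 9.7).

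Half-width of the 95% CI = t(0.975, 84) × SD × √(2/43) = 1.989 × SD × 0.2157 = 0.429 × SD.

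| Assumed SD (injections) | Half-width |
|---|---|
| 1 | 0.43 |
| 1.5 | 0.64 |
| 2 | 0.86 |
| 3 | 1.29 |

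The SD is an assumption, as the documents give none. The normal approximation gives 0.85 and 1.27 for SD 2 and 3.

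**5. Why a rate per unit time is unsuitable**

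A wait-and-extend patient who leaves at day 90 after the three loading injections contributes 3 × 360/90 = 12 injections per 360 days. The same patient, staying stable to month 12 without further injection, would have had 3. Injections are front-loaded, so a constant-rate time offset would overstate the burden of early leavers.

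**The case against.** The strongest reply is that the SAP follows the protocol's stated objectives, which concern the wait-and-extend regimen alone, and that labelled-arm information is not absent. Attendance is tabulated by group (SAP section 6), study-drug application is to be summarised (protocol 9.3), protocol 9.5.1 has no arm restriction, and doses are tracked on the CRF at every visit (protocol 5.5.4).

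Much of this stands. A reader might infer that labelled-arm burden is left out altogether, or that the trial could never estimate the reduction. The documents do not support that: the dose data are collected in both arms, and the protocol allows a two-arm summary. Nor is it right that a one-arm count says nothing about visits, because the labelled schedule fixes 14 planned visits.

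Two things remain. Attendance as n and % is neither a mean number of visits per patient nor a difference with an interval. And the protocol 9.3 summary has no counterpart in the SAP, so as written there is no planned labelled-arm injection count. That the SAP matches the objectives explains the gap without closing it: the objectives and protocol 9.5.1 differ in scope, and the SAP took the narrower one.

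**Conclusion.** The point holds in this form: SAP 6.14.3, following the one-arm objectives, narrows protocol 9.5.1, and neither document specifies a between-arm difference or confidence interval for injections or visits although lower burden is the rationale. The gap is mainly about injections, where one arm cannot show a reduction. For visits it is smaller, since a planned saving of at most about 4 of 14 follows from the schedule, assuming a patient who stays stable throughout.

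The half-widths of about 0.9 to 1.3 injections rest on an assumed SD of 2 to 3 and 43 patients per arm. They show that a useful estimate is feasible without more patients; they do not measure an error in the plan. A reader might infer that the non-inferiority conclusion on BCVA is weakened. It is not: these are secondary counts and the primary analysis does not use them. This is a change the plan should make, not a condition for the primary result.

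**What to change.** In SAP 6.14.3:

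- Report the mean number of injections and of attended visits in both arms, with the between-arm difference and 95% CI, in the same analysis set as the primary endpoint (protocol 9.1 names the Safety population for all analyses).
- State how patients who leave before month 12 are counted, so that early exit is not read as reduced burden. One option is all patients as observed, with a sensitivity analysis in 12-month completers. Do not use a constant-rate time offset.
- State whether unscheduled visits count as attended visits and, if so, confirm that the CRF records them.

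Reword the matching objectives in protocol 2.2, the synopsis and SAP 3.2 so that they cover both arms and agree with protocol 9.5.1.

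The cost is one extra table, with no added patients or procedures. The injection data are already tracked at each visit. Rewording the protocol objectives needs a written amendment (protocol 11.1), but the SAP table does not have to wait for it, because protocol 9.5.1 already covers both counts without an arm restriction.
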